## **8. Study Statistical Considerations and Analytic Plan**

### **8.1. Statistical Analyses**

A single-arm, open-label study is proposed to evaluate the primary hypothesis that participants treated with sodium thiosulfate will experience greater improvement in calcinosis activity as assessed by a change in the calcinosis visual analogue scale (VAS) after treatment compared with any change in calcinosis activity visual analogue scale during the observation period prior to treatment with sodium thiosulfate.

A intention-to-treat statistical analysis will be performed where first, the primary outcome, the change in calcinosis activity VAS score from Week 0 to Week 10 compared with any change in calcinosis activity VAS score observed during the pre-treatment period (from Week -10 to Week 0), will be analyzed using a two-tailed paired t-test. This will be reported as absolute change for the primary outcome and calculated by taking value of the time 0 score minus the time -10 score and subtracting from that the value of the time

**Abbreviated Title:** Sodium Thiosulfate (STIC)

**Version Date:** July 07, 2023

10 score minus the time 0 score. As secondary end points, we will also evaluate any changes as relative percent change and absolute percent change. Second, two-tailed paired t-tests will be performed to test for significant differences in the primary outcome for the adult and juvenile dermatomyositis patients separately. Multiple testing adjustments will be used to control for the multiple comparisons on the VAS score outcomes for the subgroup analysis.

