Two-sided paired t-tests will be performed to test for significant differences in the relative percent change in VAS score, absolute percent change in VAS score, and the secondary outcome of change in quality of life score (Physical Function Score of CHQ-PF50 for children, SF-36 for adults) from Week 0 to Week 10, compared with any change in quality of life score observed during the pre-treatment period (from Week -10 to Week 0). The secondary outcomes of changes in the components of quality of life over time, changes in functional disability over time, change in muscle strength over time, and changes in gene expression associated with therapy will also be analyzed using paired t-tests. For the gene expression analysis, multiple testing adjustments will be used to control the false discovery rate. Categorical measures of improvement in calcinosis lesions, improvement in or stabilization of myositis activity, and incidence of adverse events will be analyzed using McNemar tests. Fisher exact tests will be used to test for differences between responders and non-responders to therapy. The severity of adverse events and quantitative measures of improvement in calcinosis lesions and myositis activity will be analyzed using paired t-test or regression to control for additional covariates. Generalized linear mixed models will be considered to analyze quantitative secondary outcomes across time. Descriptive statistics, such as mean, median and standard deviation, of the primary outcome and secondary outcomes of change in VAS, change in quality of life (QOL), change in functional disability, improvement in calcinosis lesions, and change in muscle strength are also of interest and will be used to plan further studies. Prior to statistical testing, the normality of quantitative measures will be evaluated by plotting the empirical distributions of the quantitative measures to look for deviations from normality as well as using QQ-plots. For non-normally distributed endpoints, normalizing transformations, such as the log transformation, will be applied. If normality cannot be achieved by transforming the data, analogous nonparametric tests, such as the Wilcoxon Signed Rank test, will be used in the analysis. The multiple comparison adjustment method that will be used is a stepwise Bonferroni-Class Method as published in Holm (39) and Hochberg (40).

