**denotes the significance level and  $sd$  denotes the standard deviation of the differencesa.**

Mean Difference b	$\alpha=0.025$				$\alpha=0.05$			
	$sd=5$	$sd=10$	$sd=15$	$sd=20$	$sd=5$	$sd=10$	$sd=15$	$sd=20$
10	6	16	31	53	5	13	26	44
11	6	13	26	44	5	11	22	37
12	5	12	23	38	5	10	19	32
13	5	11	20	32	4	9	17	27
14	5	10	17	28	4	8	15	24
15	5	9	16	25	4	7	13	21
16	4	8	14	23	4	7	12	19
17	4	8	13	20	4	6	11	17
18	4	7	12	18	4	6	10	16
19	4	7	11	17	4	6	9	14
20	4	6	10	16	3	5	9	13
25	4	5	8	11	3	5	7	9
30	3	5	6	9	3	4	5	7

aIn between-patient standard deviation of the differences in change in calcinosis activity score between the treatment and pre-treatment periods

[figure not shown]
bThe mean of the differences in change in calcinosis activity between the treatment and pre-treatment periods

Assuming a standard deviation of 10 and a significance level of 0.05, a sample size of 13, after attrition, will provide at least 90% power to detect an improvement in calcinosis VAS score between the treatment and pre-treatment periods of at least 10 mm. If the standard deviation is 15, then a sample size of 13 will detect a mean difference of at least 15 mm. The sample size required depends on the assumed within subject correlation. Figure 2 illustrates how the required sample size will change depending on the assumed within subject correlation. Generally, the larger the assumed within subject correlation, the smaller the required sample size. For the subgroup analysis focusing on the juvenile and adult DM patients separately, a Bonferroni correction can be used to control the overall family-wise error rate to below 0.05 giving a significance level of  $0.05/2=0.025$  for each paired t-test in the subgroup analysis. Assuming that approximately the same number of juvenile and adult DM participants is enrolled in the study, a sample size of 13 for the combined group will result in at least 6 participants in each age subgroup. Assuming subgroup sizes of 6 and a standard deviation of 10, there will be at least 90% power to detect age group specific mean differences of at least 20 mm.

**Abbreviated Title:** Sodium Thiosulfate (STIC)

**Version Date:** July 07, 2023

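### With 6 patients the signed-rank fallback cannot reach the 0.025 level used to plan the subgroup tests, and the plan does not say which multiplicity procedure decides whether such a subgroup can succeed

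*Combined protocol and SAP*

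**What the plan says.** Section 8.1 puts the subgroup analysis second, after the primary test: "two-tailed paired t-tests will be performed to test for significant differences in the primary outcome for the adult and juvenile dermatomyositis patients separately", with an adjustment for multiple comparisons. Normality is judged from plots of the distributions and QQ-plots, and a two-step rule follows. First, "For non-normally distributed endpoints, normalizing transformations, such as the log transformation, will be applied". If that does not achieve normality, "analogous nonparametric tests, such as the Wilcoxon Signed Rank test, will be used in the analysis". The multiplicity method for the analysis is a "stepwise Bonferroni-Class Method as published in Holm", and the same sentence cites Hochberg as well.

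Section 8.2 plans the subgroups differently. It says that "a Bonferroni correction can be used to control the overall family-wise error rate to below 0.05", giving 0.025 per test. It expects that "a sample size of 13 for the combined group will result in at least 6 participants in each age subgroup", provided that enrolment is about equal. It then states: "Assuming subgroup sizes of 6 and a standard deviation of 10, there will be at least 90% power to detect age group specific mean differences". The smallest such difference that it names is 20 mm. Table 3 and this statement are for the two-sided paired t-test. Neither section gives a power or a smallest attainable p-value for the fallback.

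**The concern.** A signed-rank test on very few pairs has a coarse set of possible p-values, and its smallest one can lie above the significance level. If so, the test cannot be significant even when every patient improves greatly. Section 8.2 combines a small subgroup (6) with a halved level (0.025), which is where this can happen.

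Two things are at stake. First, the 90% subgroup power could be read as covering whatever test is eventually used. Second, three procedures are in play (Bonferroni in 8.2, Holm and Hochberg in 8.1), and they can give opposite answers from the same data. A non-significant subgroup result that the test could not have avoided might also be taken as lack of effect in children or in adults.

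**Working it through.** **Inputs.** From section 8.2: n = 6 per subgroup, mean difference 20 mm, SD 10 mm, two-sided level 0.05/2 = 0.025, and 13 completers, so 6+7 if split as evenly as possible. From section 8.1: signed rank as fallback, Holm or Hochberg as adjustment. In a family of two, both stepwise methods use the levels 0.025 and 0.05.

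**Step 1: the plan's own figure.** Power of the paired t-test comes from the noncentral t distribution with df = n − 1 and noncentrality (20/10) × √n. At n = 6, df = 5, the noncentrality is 2 × √6 = 4.90 and the critical value 3.163, so power is 90.9%. At n = 5 it is 78.0%. The stated n = 6 with at least 90% power is correct for the t-test.

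**Step 2: smallest signed-rank p-value.** If all n differences have the same sign, the two-sided exact p is 2/2^n.

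| n | smallest exact p | below 0.025? | below 0.05? |
|---|---|---|---|
| 5 | 2/32 = 0.0625 | no | no |
| 6 | 2/64 = 0.03125 | no | yes |
| 7 | 2/128 = 0.0156 | yes | yes |

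The normal approximation does not help at n = 6. The largest rank sum is 21, its null mean 10.5 and its null SD √(6 × 7 × 13/24) = 4.77. So z = 10.5/4.77 = 2.20 and p = 0.0277, or 0.0360 with continuity correction.

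**Step 3: what each procedure does with a 6-patient subgroup.**

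- Bonferroni: needs p ≤ 0.025. Not attainable.
- Holm, 6+6: the smaller p must first be ≤ 0.025. Neither group can do that, so nothing is rejected.
- Holm, 6+7: if the group of 7 reaches 0.0156, the group of 6 is tested at 0.05, and 0.03125 passes.
- Hochberg: if the larger p is ≤ 0.05, both are rejected. Two p-values of 0.03125 are both rejected.

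So if all twelve patients in a 6+6 split improve, Hochberg declares both subgroups significant, and Holm and Bonferroni declare neither.

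**Step 4: power of the 6-patient subgroup under the fallback** (both subgroups at 20 mm, SD 10 mm, normal data). One patient's difference is positive with probability Φ(20/10) = 0.97725. A group of 6 has p ≤ 0.05 only if all six are positive: 0.97725^6 = 0.871. A group of 7 has p ≤ 0.025 only if all seven are positive: 0.97725^7 = 0.851.

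- Bonferroni: 0%.
- Holm, 6+6: 0%.
- Holm, 6+7: 0.871 × 0.851 = 74%.
- Hochberg, 6+6: 0.871 × 0.871 = 76%.
- Hochberg, 6+7: about 86%. The group of 7 now needs only p ≤ 0.05.

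A simulation of 200,000 trials with exact p-values gave 74.1%, 75.9% and 85.6% for the last three.

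**Step 5: other shapes.** The fallback is meant for non-normal data, so the normal figures are only a reference. With the same mean and SD:

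| Shape | Holm, 6+7 | Hochberg, 6+6 to 6+7 |
|---|---|---|
| Left-skewed (negated exponential) | about 52% | 54% to 67% |
| Heavy-tailed (t with 3 df) | about 77% | 78% to 85% |
| Right-skewed (exponential) | 100% | 100% |

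In the right-skewed case no difference can fall below 10 mm. The zeros for Bonferroni and for Holm with 6+6 do not depend on shape.

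**The case against.** The strongest reply is that the fixed 0.025 belongs to sample-size planning, where Bonferroni is offered only as a possibility, while section 8.1 commits the analysis to a stepwise method. Under that method a 6-patient subgroup can pass. This stands, and it rules out two inferences that a reader might draw: that the subgroup claim becomes impossible whenever the data look non-normal, and that at least 7 patients are needed. Both are true only at a fixed 0.025. The first also skips the transformation step, and planning assumption 4 in section 8.2 openly makes the calculation conditional on normality, possibly after transformation.

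Six is also a minimum. With 13 completers one group has at least 7, so Holm with 6+6 is not the expected split. Up to 18 patients are enrolled, section 8.1 calls the analysis intention-to-treat, and withdrawn patients are still followed, so the analysed subgroups could be larger. That stands too.

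Three things remain. The two stepwise methods differ exactly where it matters, and the plan does not choose. Transformation is a limited safeguard: the analysed value is a difference of two changes and can be zero or negative, where the log (the only transformation named) is undefined. And six per group rests on roughly equal enrolment, which section 3.1 says only that the study will attempt. A 5+8 split, or one zero difference dropped by the usual signed-rank procedure, can leave n = 5, where the smallest p of 0.0625 fails under every procedure.

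**Conclusion.** The concern holds in a limited form. At the fixed 0.025 level used for planning, the signed-rank fallback cannot be significant with 6 patients, and the stated 90% subgroup power holds for the paired t-test only. Under the stepwise method of section 8.1 the outcome depends on the split and on an unmade choice. Against 90.9% for the planned t-test, power for a 6-patient subgroup is 0% (Bonferroni, or Holm with 6+6), about 74% (Holm with 6+7) or about 76% to 86% (Hochberg). These figures assume that both subgroups have the 20 mm effect with SD 10 mm and normal data, and that both are tested by signed rank. The documents do not allow an estimate of how often the fallback would be reached.

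This is worth correcting because identical data can lead to opposite subgroup conclusions. It is not a must-fix. The subgroup tests are a second-step analysis outside the listed objectives and outcome measures, and the primary test at n = 13 is not touched by this limit.

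**What to change.** Change sections 8.1 and 8.2 as follows, before subgroup results are examined:

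1. Name Hochberg as the single procedure for the two subgroup tests, and remove Holm and Bonferroni for this purpose. Hochberg is valid here because the subgroups contain different patients, so the two tests are independent. It is never less powerful than Holm or Bonferroni.
2. State that the 90% subgroup power applies to the paired t-test only. Add that the signed-rank fallback has a smallest two-sided p of 0.03125 at n = 6, and of 0.0625 at n = 5, which fails even at 0.05.
3. Report each subgroup's mean difference with a 95% CI whichever test is used, so that a non-significant result is not read as no effect.

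The cost is a few sentences, with no extra patients or data. Naming Hochberg does not help a subgroup of 5.

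Optionally, the plan could keep the t-test as the subgroup test whatever the QQ-plot shows, with signed rank as a sensitivity analysis. That removes the attainability limit, but it relies on the t-test at n = 6, where it is least protected against skew. The sponsor may reasonably decide either way.

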#### 4. Inclusion and Exclusion Criteria

Participants will be enrolled without regard to gender, race, or ethnicity. Each potential participant must meet all of the following inclusion criteria in order to be eligible to enroll in the study:

- INCL 1. At least 7 years of age
- INCL 2. Meets Bohan and Peter criteria, as modified by the International Myositis Assessment and Clinical Studies Group (IMACS), (13,14, oddis) for probable or definite DM or JDM
- INCL 3. Has extensive calcinosis, defined as calcinosis involving at least 2 extremities or the torso
- INCL 4. Has moderate to severe calcinosis, defined as having a calcinosis activity visual analogue scale score of  $\geq 3.5$  cm out of 10 cm
- INCL 5. Is willing and able to comply with the requirements of the protocol and to undergo all testing
- INCL 6. Can have IV access established to receive study infusions
- INCL 7. Myositis disease activity is stable\*
- INCL 8. Medications for myositis are stable for at least 6 weeks prior to study entry\*\*
- INCL 9. Men and women of reproductive potential must agree to use a reliable form of birth control during the 62-week duration of the study
- INCL 10. Subjects or their legal guardian must sign a written informed consent

\*Stable myositis disease activity will be defined by physician global and patient/parent global VAS that are  $< 4$  cm (35), as well as creatine kinase (CK), lactate dehydrogenase (LDH), aldolase, aspartate aminotransferase (AST), and alanine aminotransferase (ALT) that are less than or equal to 2X upper limit of normal (ULN).

\*\*If a patient has a medication for myositis changed in this window for reasons besides their myositis activity and has returned to their baseline medication use prior to enrollment they will still be eligible.

A potential participant meeting any of the following exclusion criteria is not eligible to enroll in the study:

- EXCL 1. Is pregnant or breastfeeding
- EXCL 2. Has known allergies to sodium thiosulfate, any of its components, or dextrose

**Abbreviated Title:** Sodium Thiosulfate (STIC)

**Version Date:** July 07, 2023

- EXCL 3. Has severe myositis disease activity as defined by patient/parent or physician global activity visual analogue scale score >4 cm out of 10 cm

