## 5.20. Questionnaire Assessments

Quality of life questionnaires will be administered in this study as part of the participants' clinical care and for research purposes. Generally, parents, children and adult patients will complete these assessment tools. Details of tool administration by visit, including the individual(s) completing the assessment, are provided in Table 7 found in Appendix B.

We plan to administer the following quality of life assessments in this study:

- Child Health Questionnaire - Parent Form 50 (CHQ-PF50 for pediatric participants) or Medical Outcomes Study Short Form Health Survey (SF-36; for adult participants), which include a pain score as one of their components
- Childhood Health Assessment Questionnaire (CHAQ; for pediatric participants) or Health Assessment Questionnaire (HAQ; for adult participants), to capture activities of daily living functional assessments and a pain visual analog scale score (these are also part of the IMACS activity core set measures as noted in Section 5.21)
- Calcinosis Assessment Tool (CAT), which will assess calcinosis severity and change with time (as noted in Section 5.22)
- Mawdsley Calcinosis Questionnaire, which is an experimental tool for assessing calcinosis in scleroderma patients will also be used to try and capture information on calcinosis severity.
- Patient Reported Outcomes Measurement Information System (PROMIS®) questionnaire, which will be used to capture daily life functions and health-related quality of life
- Skindex-29, which will assess dermatology-related quality of life impairment

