The validity of the calcinosis assessment tool (CAT) will be assessed by focusing on the similarity between the CAT and other disease activity measures, like the Global Physician Score (GPhS) and Patient Reported Outcomes Measurement Information System (PROMIS®). Large disagreement between the CAT and other disease activity measures would suggest that the CAT tool is not measuring improvement in calcinosis but small differences may indicate that the CAT is capturing improvement in calcinosis that the other measures are not capturing. To assess the similarity between the disease activity measures, the Spearman rank correlation coefficient between the change in the CAT responses and the change in the other disease activity measure responses will be calculated. One can then test whether this correlation coefficient is different than zero, which would suggest an association between the two measures. A kappa statistic will be calculated to assess the agreement between discrete measures in the CAT and other discrete measures of disease activity. In the case where the number of categories observed by the CAT and other discrete measures of numbers of categories differ, the comparison will be accomplished by comparing the pooled scores for all categories of

**Abbreviated Title:** Sodium Thiosulfate (STIC)

**Version Date:** July 07, 2023

the CAT to the pooled scores of each independent finding using a nonparametric Wilcoxon ranked sum statistic. Evaluation of the Mawdsley Calcinosis Questionnaire will be performed in the same manner as for the CAT. A cluster analysis will be considered to explore how well the change in VAS, along with other measures of disease activity, such as change in Global Physician Score, Patient Reported Outcomes Measurement Information System, MRI, CT scans, DEXA scans and vascular imaging, can distinguish between responders to intravenous sodium thiosulfate therapy and non-responders. Responders will be defined as those individuals who meet the primary end point and non-responders will be those individuals who fail to meet the primary end point. A Spearman rank correlation coefficient will be used to identify disease activity measures that are highly correlated and contain the duplicate information. This will aid in variable selection for future multivariate analyses to identify responders to therapy. We will also attempt to assess the responsiveness of these tools through their standardized response means.

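### The Calcinosis Assessment Tool is to be judged by agreement with named measures that are not described as measuring calcinosis, so a sound tool could be doubted or a non-specific one supported

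*Combined protocol and SAP*

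**What the plan says.** Section 2.1 lists validation of the CAT and the Mawdsley questionnaire as an additional outcome, and Section 1.6 presents validation of a calcinosis tool as a distinctive aim of the trial. The method is in Section 8.1.

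- **Comparators.** The CAT is compared with other activity measures, "like the Global Physician Score (GPhS) and Patient Reported Outcomes Measurement Information System (PROMIS"®). No others are named in that sentence.
- **Statistic.** The plan uses the "Spearman rank correlation coefficient between the change in the CAT responses and the change in the other disease activity measure responses". It adds: "One can then test whether this correlation coefficient is different than zero". No significance level, expected correlation or threshold is given. A kappa statistic is planned for discrete items, and standardized response means for responsiveness.
- **Interpretation.** "Large disagreement between the CAT and other disease activity measures would suggest that the CAT tool is not measuring improvement in calcinosis", while "small differences may indicate that the CAT is capturing improvement in calcinosis that the other measures are not capturing".
- **Mawdsley.** It is to be evaluated in the same way as the CAT.

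The physician calcinosis activity VAS, CT and DEXA appear later in Section 8.1, in a cluster analysis that will be considered. A further Spearman step there looks for duplicate information among activity measures. The sentinel lesion form is not mentioned in the validation text.

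**The concern.** A convergent-validity check needs a comparator that measures the same thing as the tool. Neither named comparator is described that way, yet the interpretive sentence draws a conclusion about calcinosis from disagreement with them. This can mislead in two directions.

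- A CAT that follows calcinosis well may move differently from myositis activity or quality of life, and be doubted for it.
- A CAT that mostly reflects pain or general wellbeing may agree with PROMIS, and be supported for it. Both are patient-reported, in an open-label trial, and the CAT contains a pain VAS (Section 5.22).

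At stake is whether later calcinosis trials adopt or discard these two tools.

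**Working it through.** **Step 1. What the named comparators measure.** Section 5.20 describes PROMIS as a questionnaire "which will be used to capture daily life functions and health-related quality of life". The Global Physician Score is not defined. The physician global in the core set (Section 5.21) is a myositis activity item. Section 8.1 lists the Global Physician Score separately from the change in VAS, so the myositis global is the likelier reading. It remains an inference.

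**Step 2. Whether the protocol treats the constructs as one.** It does not.

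- Section 4: "Stable myositis disease activity will be defined by physician global and patient/parent global VAS" below 4 cm, together with muscle enzyme limits. The same section requires a calcinosis activity VAS of at least 3.5 cm. A patient must be low on one scale and at least moderate on the other.
- Section 3.4 wants CT to show that changes on physician and patient globals come from reduced calcinosis burden and not only from other effects.
- Section 5.8 calls CT quantification critical for deciding whether improvement noted by patients or physicians reflects a real change in burden.
- Section 1.4 reports pain relief too fast to be explained by reduced burden.

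**Step 3. Which calcinosis-specific measures are available, and when** (Appendix B, Tables 4 and 7; Sections 3.4, 5.4 and 5.8).

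| Measure | Weeks | Limits |
|---|---|---|
| CAT | Screening, -10, -4, 0, 2, 4, 6, 8, 10, 24, 62 | tool under validation |
| Physician calcinosis activity VAS | as CAT, except -4 | unblinded; its scoring includes pain |
| DEXA lesion calcium | -10, 0, 6, 10, 24, 62 | misses lesions over bone; baseline may be a scan up to 6 months old |
| Sentinel lesion form | -10, 0, 6, 10, 24, 62 | up to 5 lesions |
| CT volume | 0, 10, possibly 62 | Week 0 scan is not done if there was one in the prior year |

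**Step 4. What about 13 patients can show.** The validation has no sample size of its own; 13 comes from the primary analysis. That figure reproduces: difference 10 mm, SD 10 mm, paired t-test, two-sided 0.05, n = 13 gives power 91.1%. With 25% dropout, 13 / 0.75 = 17.3, so 18 enrolled.

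Assume one change score per patient, complete data and two-sided 0.05. The critical correlation (t approximation) is t / √(n − 2 + t²).

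- n = 13: t = 2.201, so 2.201 / √(11 + 4.844) = 0.553.
- n = 18: t = 2.120, so 2.120 / √(16 + 4.494) = 0.468.

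Precision at n = 13, using the Fisher transform with standard error √((1 + ρ²/2)/(n − 3)):

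- Observed 0.5: standard error √(1.125/10) = 0.335; 95% interval −0.11 to 0.84.
- Observed 0.7: standard error √(1.245/10) = 0.353; 95% interval 0.17 to 0.92.

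Chance of a significant Spearman correlation (simulation, 100,000 bivariate normal samples). The true correlations are assumed; none comes from the documents.

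| Assumed true correlation | n = 13 | n = 18 |
|---|---|---|
| 0.3 | 15% | 21% |
| 0.5 | 38% | 52% |
| 0.7 | 73% | 88% |
| 0.8 | 90% | 98% |

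A non-significant result is thus likely for a modest true correlation and still happens 27% of the time at 0.7. Even an observed 0.5 is compatible with no association. The test against zero cannot carry the validation alone, and the choice of comparator matters.

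**The case against.** The strongest reply is that the comparator list is illustrative. The word 'like' leaves it open, Section 8.1 later counts CT and DEXA among measures of disease activity, and Sections 2 and 3.3 plan to evaluate imaging, patient-reported and physician tools together. This stands as far as it goes: the plan does not exclude calcinosis-specific comparators. But it does not commit to any, and an open list allows the choice to be made after the results are seen.

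Three stronger readings are tempting and should not be drawn.

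- *That a good CAT would be declared invalid.* The text says only that disagreement would suggest a problem. It sets no threshold, lets small differences count in the CAT's favour, and nowhere equates a non-significant correlation with invalidity.
- *That the entry limit leaves the physician global with no room to move, which would destroy the correlation.* The limit applies to the level at entry, while the analysis uses change. Improvement is capped below 4 cm from the entry value, but worsening is not, and no distribution is given. PROMIS has no entry limit.
- *That the correlation with the named comparators must be low.* Sections 1.4 and 5.19 expect gains in strength, pain and the underlying myositis, so shared change is plausible. Nor is a high correlation with imaging assured: Section 10.1.2.5 describes a patient whose surface findings worsened while CT evidence led to her being assessed as improved.

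**Conclusion.** The point holds as a risk of misreading in either direction. The only plan for a stated outcome names two comparators not described as measuring calcinosis, and interprets disagreement with them as evidence about calcinosis, although the protocol itself keeps the constructs apart. It should be changed, but it concerns an additional outcome and touches neither the primary efficacy inference nor safety.

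The firm figures are the threshold of about 0.55 at n = 13 (0.47 at n = 18) and the wide intervals, given two-sided 0.05 and one complete change score per patient. The power figures are illustrative only. The conclusion also rests on reading the Global Physician Score as myositis activity. If it means a calcinosis rating, that half of the concern falls away, but the definition is still needed and PROMIS remains.

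**What to change.** In Section 8.1:

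1. Define the Global Physician Score.
2. Name the physician calcinosis activity VAS as the main convergent comparator for change in both the CAT and the Mawdsley questionnaire.
3. Name supporting comparators: DEXA lesion calcium and the sentinel lesion form at Weeks -10, 0, 6, 10, 24 and 62; CT volume where Week 0 and Week 10 scans both exist, flagging any baseline scan taken up to a year earlier; and the CAT against the Mawdsley.
4. Keep the Global Physician Score and PROMIS as secondary measures of related but different constructs.
5. Apply the large-disagreement sentence only to the calcinosis-specific set.
6. Report every correlation with a confidence interval and do not rely on the test against zero.

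No new data are needed. The cost is SAP wording and a few more correlations from about 13 patients, each imprecise. The calcinosis VAS is not an independent gold standard: its scoring takes account of pain, and Table 7 has a physician review the CAT, so the VAS rater may have seen it. The imaging measures are therefore worth having despite fewer time points.
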